2 STUDY SUMMARY AND AIMS

The purpose of this study is to determine the incidence, risk factors and adverse events consequent upon atrial fibrillation after cardiac surgery, as well as the association between prior atrial fibrillation and postoperative atrial fibrillation. The study uses information from local Cardiac Surgical Programs to describe the preoperative medical state and immediate post-operative state. Additionally, information from the post-discharge period will be provided by CHIA, by matching the two sources of information using HIPAA-waived data such as medical record number, date of birth, gender and last name. Once matched, the data are stripped of identifiers.

2.1 Study Design:

We will employ a retrospective cohort design, examining patients who underwent cardiac surgery at Cardiac Surgical Programs in Massachusetts between 1/1/2012 and 12/31/2016, with a follow-up period that extends to 12/31/2017. The study examines the risk factors and incidence of post-operative atrial fibrillation, stroke and other focal neurological events after discharge from hospital.

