7 STATISTICAL ANALYSES

7.1 General

Baseline and demographic characteristics will be summarized using descriptive statistics (means, standard deviations or median, interquartile ranges for continuous variables such as age and percentages for categorical variables such as race and ethnicity. When deemed appropriate, they will be compared using Chi-square test, Fisher's exact test, two-sample t test, and Wilcoxon rank-sum test between groups. For each binary outcome we will report odds ratios with 95% confidence intervals and give a two-sided p-value for statistical significance. For analysis of the pre-specified subgroups (primary outcome only) we will report relative risks with 99% confidence intervals with two-sided p-value.

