7.1.1 Primary Aims

The standard Cox proportional hazards model will be used to model time to first atrial fibrillation occurrence and time to first stroke or other focal neurologic event, after discharge from hospital,

respectively. The potential risk factors included will be selected based on their univariate association with first event status, as well as clinical significance. Hazard ratios with 95% confidence intervals will be reported with a two-sided p-value for statistical significance. The proportional hazard assumption will be evaluated using graphical tool, and by including time dependent covariate terms.

Since there might be repeated occurrences of atrial fibrillation and stroke or other focal neurologic event for each patient, we will use the Andersen-Gill (AG) model and the Prentice, Williams and Peterson (PWP) models to analyze recurrent events data. The AG model is suitable when the interest is in the overall effect on the intensity of the occurrence of a recurrent event. The PWP models allow us to evaluate the effects of risk factors for the kth event after discharge from hospital, as well as the effects of risk factors for the kth event since the time from the previous event (47). Hazard ratios with 95% confidence intervals will be reported with a two-sided p-value for statistical significance. For time-to-event data analyses, death will be considered a censoring event.

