12 APPENDIX: SHELL TABLES AND FIGURES

12.1 Tables

Table 1: Characteristics of the study participants.

Table 2: Comparison of characteristics of patients with post-discharge atrial fibrillation and those patients who did not have post-discharge atrial fibrillation

Table 3: Time-adjusted risk of post-discharge atrial fibrillation

Table 4: Time-adjusted risk of post-discharge stroke

Table 5: Time-adjusted risk of post-discharge mortality

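### The covariate screen in 7.1.1, read literally, compares ever against never having an event and ignores time at risk, so risk factors that also raise mortality can be missed

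*Combined protocol and SAP*

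**What the plan says.** Section 7.1.1 (Primary Aims) sets the model: "The standard Cox proportional hazards model will be used to model time to first atrial fibrillation occurrence", and likewise for first stroke or other focal neurologic event. On deaths it says: "For time-to-event data analyses, death will be considered a censoring event". The selection rule is that potential risk factors will be "selected based on their univariate association with first event status", with clinical significance as a second basis. It names no univariate test and no threshold, and does not say how the statistical and clinical criteria combine.

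Section 2.1 places surgery "between 1/1/2012 and 12/31/2016, with a follow-up period that extends to 12/31/2017". Potential follow-up is therefore about 1 year for the last patients operated on and about 6 years for the first.

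The only univariate group tests named in the plan are in Section 7.1, where baseline characteristics are "compared using Chi-square test, Fisher's exact test, two-sample t test, and Wilcoxon rank-sum test between groups". Table 2 in Section 12.1 is titled "Comparison of characteristics of patients with post-discharge atrial fibrillation and those patients who did not have post-discharge atrial fibrillation". No log-rank or univariate Cox screen is named. In Section 7.1.2 the Poisson models carry a follow-up offset, but their covariates are chosen on unspecified univariate tests plus clinical significance.

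**The concern.** The endpoint has two parts, whether the event occurred and when observation stopped. The final model uses both; the screen, as worded, uses only the first. A patient who dies event-free in the first year counts as a non-event on the same footing as one observed event-free for six years.

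This can go wrong in two directions. A factor that raises both the event rate and the death rate loses event opportunities through death, so its ever-event odds ratio is pulled toward or below 1 and it may fail the screen. A factor associated only with operation year inherits the difference in follow-up and may pass with no effect at all.

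The first direction matters more. A covariate left out cannot be restored by the Cox model that follows, and identifying risk factors is the stated primary aim. The issue arises among purely preoperative variables too.

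**Working it through.** **Inputs from the documents.** N = 50,000, two-sided 0.05 and a 25% reference AF rate (Section 4); follow-up window (2.1); death as censoring (7.1.1). 7.1.1 sets no selection threshold, so I take |z| > 1.96 from the general 0.05 level.

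**Assumptions, not in the documents.** Constant hazards; follow-up uniform on 1 to 6 years; reference death rate μ = 0.03/yr; AF rate λ = 0.08/yr, or λ = 0.0093/yr for stroke, which gives 3% ever-stroke; factor prevalence 3% or 8%.

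**The plan's own figure.** Section 4's effect size reproduces: (1.960 + 0.842) × √(1/4,000 + 1/46,000) = 0.0462, against 0.046 stated. The screening question does not affect it.

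**Formulas.** With s = λ + μ, the probability of an observed first event is

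P = (λ/s) × [1 − (e^(−s) − e^(−6s))/(5s)].

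The status z is ln(OR) over its standard error from the expected 2×2 table. The univariate Cox z is approximated by ln(HR)/√(1/d1 + 1/d0), where d1 and d0 are expected events with and without the factor.

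**One case in full: AF HR 1.3, death ratio 4, prevalence 3% (1,500 v 48,500 patients).**
- Reference: s = 0.11, P = 0.727 × (1 − 0.689) = 22.6%, near Section 4's 25%.
- With the factor: λ = 0.104, μ = 0.12, s = 0.224, P = 0.464 × (1 − 0.481) = 24.1%.
- OR = 1.087. Expected events are 361.6 and 10,967.7; non-events are 1,138.4 and 37,532.3. The standard error of ln(OR) is 0.0613, so status z = 0.0833/0.0613 = 1.4.
- Cox z = 0.2624/√(1/361.6 + 1/10,967.7) = 4.9.

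**Range for AF, 3% prevalence (status z / Cox z).**

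| True AF HR | Death ratio 2 | 3 | 4 | 5 | 6.7 |
|---|---|---|---|---|---|
| 1.2 | 2.2 / 3.5 | 1.0 / 3.4 | −0.1 / 3.3 | −1.0 / 3.2 | −2.5 / 3.1 |
| 1.3 | 3.7 / 5.2 | 2.5 / 5.0 | 1.4 / 4.9 | 0.3 / 4.8 | −1.3 / 4.6 |
| 1.5 | 6.6 / 8.4 | 5.3 / 8.2 | 4.1 / 8.0 | 2.9 / 7.8 | 1.2 / 7.6 |
| 2.0 | 13.1 / 16.0 | 11.5 / 15.6 | 10.1 / 15.3 | 8.8 / 14.9 | 6.7 / 14.4 |

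At 8% prevalence, HR 1.2 with death ratio 3 gives 1.6 / 5.4, and HR 1.3 with ratio 4 gives 2.2 / 7.8.

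**Stroke, 3% ever-event, 8% prevalence.** HR 1.3 with death ratio 2 gives 2.3 / 3.0. With ratio 3 it gives 1.6 / 2.9, a chance of passing of about 37% against 84%. HR 1.5 with ratio 3 gives 3.4 / 4.8.

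**Operation year, no true effect.** Patients operated on in 2012 have 5 to 6 years of potential follow-up; those in 2016 have 1 to 2. Ever-AF is 33.0% v 11.0%, OR about 4.0.

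**The case against.** The reading is not certain. In survival work, event status is also the usual name for the event/censoring indicator in a univariate Cox model. The plan never says that Table 2 is the screen: that table and the Section 7.1 tests are presented as descriptions of baseline characteristics. Section 7.1.2 mentions only univariate tests, so its weakness is inferred from silence. This stands as a reason for moderate confidence in the reading. It does not remove the point, because no time-aware screen is named anywhere and the literal rule is the ever/never one.

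A reader might infer that true risk factors will be dropped. The documents do not support that. No threshold is set, clinical significance is a second basis for selection, and conditions such as heart failure or dialysis could well be kept on that ground. Prior AF is named as the main risk factor in both primary aims and is unlikely to be screened out. The table shows that loss needs a weak factor with a strong mortality effect, or a rarer outcome. What remains is that the clinical clause has no rule: if both criteria must be met, it rescues nothing.

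A reader might also infer that follow-up length will be reported as a risk factor. A wrongly admitted factor then enters a Cox model that accounts for time at risk, so its hazard ratio should be near 1. That is a selection error, not a wrong final estimate.

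Finally, a reader might infer serious confounding of the prior-AF hazard ratio. Take an omitted factor with HR 1.3, present in 3% of patients without prior AF and assumed three times as common with it. Simple external adjustment gives a bias factor of (1 + 0.09 × 0.3)/(1 + 0.03 × 0.3) = 1.027/1.009 = 1.018; at five times as common, 1.045/1.009 = 1.036. That is small per factor, and Section 7.6 adds negative-control and E-value checks.

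**Conclusion.** The concern holds as a mismatch between screen and model. As worded, the screen ignores time at risk, while follow-up varies about sixfold and death shortens it. Risk factors that also raise mortality can be missed or look reversed at that step.

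For AF at 3% prevalence, the loss is confined to weaker factors: HR 1.2 from a death ratio a little above 2, and HR 1.3 from about 3.5. HR 1.5 passes up to about 5, and HR 2.0 at every ratio tried. For stroke, HR 1.3 is already more likely than not to be missed at a death ratio of 3, even at 8% prevalence. These sizes rest on the assumed constant hazards, event and death rates, prevalences and 0.05 threshold. The documents supply the sample size, the follow-up window and the handling of death.

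The plan should be changed, but nothing here shows that a particular factor will be lost or that the reported hazard ratios will be materially wrong.

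**What to change.** In Section 7.1.1, replace screening on event status with a univariate Cox model for the same time-to-first-event endpoint, using the same time origin and censoring as the final model. State that clinically important factors are kept whatever the screen shows, and give the screening threshold. In Section 7.1.2, screen with univariate Poisson models that carry the follow-up offset.

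Event rates per person-year beside the crude comparison in Table 2 would help readers but are optional, since Tables 3 to 5 are already headed as time-adjusted.

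The cost is a sentence or two in the SAP and a different screening call in the analysis program. No additional data are needed.

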7.1.2 Secondary Aims

Means and standard deviations will be estimated for count outcomes. We will report the two-sided p-value for statistical significance of the difference in means of count outcomes.

The frequencies of atrial fibrillation and stroke or other focal neurologic event will be modeled with Poisson regression with the length of follow-up time as the offset. Potential risk factors included in this model will be selected based on univariate test results, as well as clinical significance. Logistic regression will be used to model the incidence of all-cause and stroke-related mortality after cardiac surgery, respectively.

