12.2 Figures

Figure 1: CONSORT diagram

Figure 2: Time course of the occurrence of post-discharge AF

Figure 3: Time course of the occurrence of post-discharge stroke stratified by occurrence of post-discharge AF

Figure 4: Time course of the occurrence of post-discharge mortality stratified by occurrence of post-discharge AF

Table 1: Characteristics of the study participants. Data are reported as number and percentage, or median and 10-90% quantiles, as appropriate

CSP = Cardiac surgical program

CHIA = Center for Health Information and Analysis

	Patient characteristic	Data source	Source variable
0	Demographics		
1	Age at surgery (years; N/%)	CSP	Calculated
2	<50		SurgDt - DOB
3	50-59		
4	60-69		
5	70-79		
6	≥80		
7	Gender (Male; N/%)	CSP	Gender
8	Race (Caucasian; N/%)	CSP	RaceCaucasian
9	Ethnicity	CSP	Ethnicity
10	Height (cm; mean/SD)	CSP	HeightCm
11	Weight (kg; mean/SD)	CSP	WeightKg
12	BMI (kg/m ² ; N/%)	CSP	Calculated
13	<20		
14	20-24.9		
15	25-29.9		
16	30-34.9		
17	≥35		
18	Payor		
19	Government	CSP	PayorGov
20	Commercial	CSP	PayorComm
21	HMO	CSP	PayorHMO
22	Prior Medical History		
23	Atrial fibrillation	CSP and CHIA	ArrhythAFib, ArrythAFibDur, ArrythAFibTy
24	Atrial flutter	CSP and CHIA	ArrhythAFlutter
25	History of arrhythmia	CSP and CHIA	
26	Heart block or sick sinus syndrome	CSP and CHIA	ArrhyVtachSicSinSyn, ArrhyTHB, ArrhyVtachHrtBlk, ArrhythSSS

27	VT/VF	CSP and CHIA	ArrhyVtach, ArrhythVV
28	Smoker past or current	CSP	TobaccoUse, CigSmoker, SmokCurr
29	COPD	CSP	ChrLungD
30	Diabetes	CSP	Diabetes, DiabCtrl
31		NIDDM	
32		IDDM	
33	Dyslipidemia	CSP	Dyslip
35	Dialysis	CSP	Dialysis
36	Hypertension	CSP	Hypertn
37	Peripheral vascular disease	CSP	PVD
38	Sleep apnea	CSP	SlpApn
39	Alcohol use	CSP	Alcohol
40	Cerebrovascular disease	CSP	CVD
41	Prior CVA	CSP	CVA, CVAWhen
42	TIA	CSP	CVDTIA
43	Carotid Stenosis	CSP	CVDCarSten
44	Prior carotid surgery	CSP	CVDPCarSurg
45			
46	Medications		
47	ACEI/ARB	CSP	MedACEI48
48	Anticoagulant or anti-platelet drug	CSP	MedACoag
49	Amiodarone	CSP	MedAmiodarone
50	Aspirin	CSP	MEDASA
51	Beta blocker	CSP	MedBeta
52	Calcium channel blocker	CSP	MedCChanTher
53	Antiarrhythmic	CSP	MedAarry
54	Coumadin	CSP	MedCoum
55			
56	Prior Cardiac Status		
57	Heart failure		PriorHF
58	Prior MI		PrevMI, MIWhen
59		Past	
60		Recent	
61	Prior CABG surgery	CSP	PrCAB

62	Prior mitral valve surgery	CSP	PrValveProc1, PrValveProc2, PrevProcMVReplace, PreProcMVRRepair

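### With deaths censored and no competing-risk method named, the AF and stroke time-course curves (and any absolute risks in Tables 3-4) would overstate incidence if they follow that rule

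*Combined protocol and SAP*

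**What the plan says.** The rule on deaths closes section 7.1.1: "For time-to-event data analyses, death will be considered a censoring event". It carries no exception. The models in that section are Cox models for first events ("The standard Cox proportional hazards model will be used to model time to first atrial fibrillation occurrence and time to first stroke", with other focal neurologic events added to stroke) and Andersen-Gill and PWP models for recurrent events. Their stated output is hazard ratios with 95% confidence intervals.

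The secondary aims are handled differently in section 7.1.2. Event frequencies are "modeled with Poisson regression with the length of follow-up time as the offset". Deaths have their own models: "Logistic regression will be used to model the incidence of all-cause and stroke-related mortality after cardiac surgery, respectively".

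The shells in section 12 list displays with a time axis or a risk measure:

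- the AF curve, listed as "Figure 2: Time course of the occurrence of post-discharge AF";
- the AF table, listed as "Table 3: Time-adjusted risk of post-discharge atrial fibrillation";
- the stroke curve, listed as "Figure 3: Time course of the occurrence of post-discharge stroke stratified by occurrence of post-discharge AF";
- the stroke table, listed as "Table 4: Time-adjusted risk of post-discharge stroke".

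No estimator is named for the two figures, and risk is not defined for the two tables. The sensitivity analyses in section 7.6 cover negative controls, E-values, stratified models and agreement between the recurrent-event models. None deals with death as a competing event.

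**The concern.** A patient who dies without AF or stroke can no longer have either. Censoring such a patient is harmless when the target is the cause-specific hazard ratio. It is not harmless when the target is the proportion of patients who have the event by a given time. One minus Kaplan-Meier with deaths censored estimates that proportion as if nobody died, so it exceeds the real proportion whenever some patients die first.

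Follow-up is long enough for this to count. Operations run from 2012 to 2016 and follow-up ends on 12/31/2017, so patients have about 1 to 6 years, and Table 1 uses intervals out to 4-5 years. Because follow-up is staggered, a multi-year time course needs a time-to-event estimator, and the only rule the plan gives for such analyses is to censor deaths. At stake are the descriptive incidence figures that readers would take from the curves.

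**Working it through.** **The plan's own figure.** The plan computes nothing on this point. Its one calculated figure, in section 4, reproduces: (1.960 + 0.842) × √(1/4,000 + 1/46,000) = 0.0462, against 0.046 stated, and from 25% this gives 27.0%, a 2-point difference. It does not depend on how deaths are handled.

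**Inputs.**

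- Death-censored 5-year AF risk *r* = 25%. This is illustrative; 25% is the section 4 figure for postoperative AF without prior AF and the top of the 3-25% range in section 1.2.
- Death-censored 5-year stroke risk *r* = 5%. Assumed.
- 5-year mortality *m* = 5% to 40%. Assumed, because the documents give no post-discharge mortality.
- Constant, independent hazards and complete recording of deaths. Assumed.

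**Formulas.** With event hazard *a* = −ln(1−*r*)/5 and death hazard *d* = −ln(1−*m*)/5:

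- one minus Kaplan-Meier = 1 − exp(−5*a*) = *r*
- cumulative incidence = *a*/(*a*+*d*) × [1 − exp(−5(*a*+*d*))]

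**Worked case.** For *r* = 25% and *m* = 20%, 5*a* = 0.2877 and 5*d* = 0.2231. Cumulative incidence = 0.2877/0.5108 × (1 − 0.75 × 0.80) = 0.5632 × 0.40 = 22.5%. The excess is 2.5 points.

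**Results at 5 years.**

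| Assumed 5-year mortality | AF: cumulative incidence when death-censored risk is 25% | Relative excess | Stroke: cumulative incidence when death-censored risk is 5% | Relative excess |
|---|---|---|---|---|
| 5% | 24.4% | 2.5% | 4.9% | 2.6% |
| 10% | 23.8% | 5.1% | 4.7% | 5.3% |
| 20% | 22.5% | 11.0% | 4.5% | 11.5% |
| 30% | 21.2% | 17.9% | 4.2% | 18.7% |
| 40% | 19.8% | 26.2% | 3.9% | 27.4% |

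In absolute terms the excess is 0.6 to 5.2 points for AF and 0.1 to 1.1 points for stroke.

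**Results at 1 year.** With 1-year mortality assumed at 2% to 5%, a death-censored 1-year risk of 25% corresponds to 24.8% to 24.4%, a relative excess of about 1% to 2.5%.

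**Which outputs the rule reaches.**

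| Output | Inflated by censoring deaths? |
|---|---|
| Cox, Andersen-Gill and PWP hazard ratios | No; they are cause-specific |
| Poisson rates per follow-up time | No |
| Table 1 counts by interval | No |
| Figures 2 and 3 | Yes, if drawn under the section 7.1.1 rule |
| Tables 3 and 4 | Only if they hold absolute risks computed under that rule |
| Table 5 and Figure 4 (mortality) | Not applicable; death is the event |

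**The case against.** The strongest reply is that the plan never says it will use Kaplan-Meier. The censoring sentence follows models whose output is hazard ratios, for which it is a proper choice. Tables 3 and 4 may hold only hazard ratios; Table 5 on mortality has the same form of title. All of this stands, and it makes the point conditional. It does not remove it, because the figures need some estimator and the stated rule leads to the biased one.

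A reader might infer three stronger things that the documents do not support:

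- *That the primary hazard ratios are wrong.* They are not. Cause-specific hazard ratios suit aims about risk factors.
- *That the frequency aims are inflated.* They are served by Poisson rates and interval counts, which this rule does not inflate.
- *That the difference between patients with and without prior AF would be exaggerated.* This can be made to happen on paper. Take a cause-specific hazard ratio of 1.5, 5-year mortality of 30% with prior AF against 15% without, and a death-censored risk of 25% without prior AF. The risk difference is then 10.0 points by one minus Kaplan-Meier and 6.7 by cumulative incidence. Section 1.2 does link preoperative AF to higher mortality. But no listed figure or table title compares absolute AF or stroke risk by prior AF: Figure 2 is listed without strata, Figure 3 is stratified by post-discharge AF, and section 7.1.1 reports risk-factor effects as hazard ratios.

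Two further objections also stand. Only 2012 operations can reach 5 years, so the larger excesses belong to the thinnest part of the curves. And the direction depends on deaths being captured. Table 1 takes 30-day, 1-year and 5-year mortality from the surgical programs, and the minimum merge fields in section 10 include no death date. That does not show that deaths are missing, but the source of late deaths is unclear. Patients whose deaths go unrecorded stay in the risk set, which shrinks the overstatement; if AF or stroke events are lost as well, the bias could reverse.

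**Conclusion.** The point holds for the time-course curves in Figures 2 and 3, and for Tables 3 and 4 to the extent that they report absolute risks. If these follow the only stated rule and deaths are recorded, the direction is certain: incidence is overstated. The size cannot be fixed from the documents. It is minor at 1 year or at low mortality, and reaches about a quarter of the reported risk only at the top of the assumed 5-year mortality range. It is worth settling before the curves are drawn, and it gives no reason to change the primary models.

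**What to change.** - In section 7.1.1, keep the models and label their hazard ratios cause-specific.
- Add one sentence: Figures 2 and 3, and any absolute AF or stroke risk in Tables 3 and 4, use the Aalen-Johansen cumulative incidence with death as a competing event.
- Define the risk measure in Tables 3 and 4. If it is a hazard ratio only, say so.
- State where post-discharge death dates come from and how complete they are. The new estimator needs the same dates that the censoring rule already presupposes.
- A Fine-Gray model is optional; the aims do not require it.

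The analysis needs standard software and no design change. The practical burden is settling the source of death dates. The visible effect is that reported incidences become slightly lower.

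This does not by itself make Figure 3 sound. Its strata are defined by AF that occurs during follow-up, and Aalen-Johansen curves drawn within those strata would inherit that problem, which needs its own solution.
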